The sarcoplasmic reticulum (SR) is the muscle cell's production and function center. It is made mostly of a phospholipid (fatty) layer that is also integral to its function. Fatty acid synthase (FAS) and choline/ethanolamine phosphotransferase 1 (CEPT1) are two proteins involved in the production of this phospholipid layer. Depending on the activity of these proteins, this phospholipid layer can assimilate more of certain types of phospholipids, mainly phosphatidylethanolamine (PE) and phosphatidylcholine (PC). Phosphatidylethanolamine is the phospholipid species assimilated when FAS and CEPT1 are active. The more active these proteins, the more PE is present in the SR layer. The main alternative to PE is phosphatidylcholine. More of this phospholipid species is assimilated into the SR when the above proteins are not active. Each of these phospholipids carries a different structure and with it, different functional properties, so depending on which type of phospholipid is more abundant, the overall structure and function of the SR is varied.

Interestingly, our new data show that high fat feeding leads to increased fatty acid synthase activity in mice. In humans, we have found that FAS is increased in the skeletal muscle of obese, yet healthy subjects, while it is decreased in metabolically compromised obese subjects (Fig 1). Furthermore, we have found that surgically induced weight loss decreases both FAS and CEPT1 (Fig 2). These results suggest that FAS and CEPT1 are part of a phospholipid production pathway brought on by high fat feeding or obesity to preserve the function of the sarcoplasmic reticulum. This fails in those who progress to metabolic decompensation (the obese 'abnormal' in Fig 1A).

Given the function of these proteins, these studies suggest that the phospholipid composition may also be altered in metabolically compromised individuals when compared with normal subjects. Indeed, this hypothesis was supported by our findings of altered phospholipid composition in mice with artificially lowered activity of these proteins. There was more PC than PE in the sarcoplasmic reticulum of these mice when fed a high fat diet.

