But what does the sarcoplasmic reticulum have to do with blood sugar control? It turns out that insulin sensitivity is related to the activity of a protein that interacts with the sarcoplasmic reticulum, called sarco/endoplasmic reticulum ATPase (SERCA). The main function of SERCA is to store calcium in the sarcoplasmic reticulum in order to allow the muscle to relax. This resets the muscle to allow for repeated muscle contraction. However, SERCA is only functional when actively associated with the phospholipid layer of the SR. Calcium also seems to regulate insulin sensitivity in the muscle cell through the proteins CaMKK β , AMPK, and AS160 (Fig 4). When SERCA is not active and therefore calcium is not stored in the SR, muscle cells are more insulin sensitive. When SERCA is active and therefore calcium is stored away and not available in the cytosol of the cell, muscle cells are more insulin resistant.

[figure not shown]

Fig 1. FAS mRNA levels in human skeletal muscle. *P<0.05 vs. obese abnormal by Tukey's post hoc test. B. FAS mRNA in mice from Fig 1A of reference 4.

[figure not shown]

Fig 2. FAS and CEPT1 protein in skeletal muscle biopsies from 16 obese human subjects before and after 20% weight loss induced by gastric bypass.

How do these findings relate to the composition of the sarcoplasmic reticulum? Our studies have shown that SERCA has lower activity when the composition of the sarcoplasmic reticulum is comprised of more PC than PE. Mice that are artificially induced to have this altered SR composition through inactivation of FAS are found to have muscle weakness, but this is in exchange for improved blood sugar control. In normal mice with functioning FAS, the PE to PC ratio is preserved and muscle strength is normal, but at the cost of reduced insulin sensitivity. This suggests that insulin sensitivity may be determined by the ratio of PC to PE in muscle tissue, based upon the activity of SERCA. When there is more PC than PE, the activity of SERCA is lower and thus muscle function is compromised, but the cell's sensitivity to insulin is higher. Conversely, when there is more PE than PC, the activity of SERCA is higher and thus muscle function is preserved, but the cell's sensitivity to insulin is lower. Our conclusion from these observations is that the muscle cell sacrifices insulin sensitivity for muscle function when called upon to do so. The muscle cell's first priority is to contract, not to be sensitive to insulin.

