Study Design. We will perform a cross-sectional study of age-matched, sedentary lean controls and individuals with the metabolic syndrome, recruited in part from a large database of subjects screened for our recently completed clinical trial (manuscript in preparation) involving metabolic syndrome (NCT00455403).

Eligibility Criteria

Control subjects

Inclusion:

1. Sedentary: No routine exercise; walking <10,000 steps per day
2. Age >18 and <65
3. Body Mass Index (BMI) <32
4. Healthy by physical exam (patient is devoid of major acute or chronic illness)
5. No significant abnormality in screening labs

Exclusion:

1. Currently on any significant prescription medications other than oral contraceptives in women
2. Currently Pregnant
3. Current Tobacco use

Subjects with the Metabolic Syndrome**Inclusion**

1. Sedentary: No routine exercise; walking <10,000 steps per day
2. Age >18 and <65
3. Body Mass Index (BMI) >30
4. Meet at least three of the following ATP III criteria for the metabolic syndrome:
 - a. waist circumference > or = 40 inches in men, > or = 35 inches in women
 - b. blood triglycerides > or = 150 mg/dL
 - c. blood HDL cholesterol <40 mg/dL in men, <50 in women
 - d. blood pressure > or = 130 mmHg systolic, or > or = 85 mmHg diastolic
 - e. fasting blood sugar > or = 100 mg/dL

Exclusion

1. Diagnosed with Type 2 diabetes, coronary artery disease, cancer, liver, lung, or kidney disease or any other major illness
2. Currently on any significant prescription medications other than:
 - a. oral contraceptives in women
 - b. More than two standard medications for stage 1 hypertension in men or women (blood pressure 140-159/90-99)
3. Currently Pregnant
4. Current Tobacco use

Study Plan and Procedures

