Screening. Potential subjects will be interviewed, the protocol will be explained in detail, then risks and benefits of involvement will be discussed. Those subjects interested in participating will be given ample time to review the informed consent, to ask questions of any member of the study team, and will sign the informed consent prior to any study procedures being conducted. Subjects will have a complete history and physical examination (including measurement of blood pressure according to a standard protocol and determination of height, weight and waist circumference, all performed by experienced personnel in the Washington University IRU) or the study coordinator. A CBC, CMP, HbA1c, and a lipid panel will be performed to determine whether the patient meets the inclusion criteria and does not meet any exclusion criteria. Individuals who have one or more exclusions will be informed of their test results but will not proceed further. If the patient meets the inclusion and does not meet the exclusion criteria specified above at the screening visit, he or she will be scheduled for three subsequent visits, as depicted in the schedule of events.

Rescreening Visit. If potential subject fails screening based upon a single criterion, i.e. a lab result or blood pressure that is thought not to be reflective of prior results based on history, at the discretion of the investigator the screening procedure may be repeated once.

Study procedures. Patients who provide informed consent, and who meet the inclusion criteria and do not meet the exclusion criteria will receive 2 phone calls (Visits 2 and Visit 3) approximately 1 week apart and will return to the study site for a final subsequent visit. At visits 2 and 3 study staff will be verifying no change in eating or exercising habits, as well as no change in medications or health status. Visit 4 will interview subjects to determine no changes in

eating or exercising habits, no changes in medications or health status and the following procedures: lab work (HbA1c, Lipid panel, fasting glucose and insulin levels, as well as 3 vials of blood for future use), an oral glucose tolerance test including an insulin level with each draw, a DEXA scan, and a muscle biopsy. The schedule of events, as well as explanations of each procedure is outlined below.

	Comp-SR Schedule of Events					
Procedure	Screening	*Rescreen	Phone visit	Phone visit	Final visit	
	Week 1		Week 2	Week 3	Week 4	
Fasting (10-12 hours)	X	X			X	

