Muscle Biopsy. This procedure will be performed on the final visit. A member of the study team will obtain a sample of muscle tissue from the patient's thigh (vastus lateralis muscle). This involves numbing the skin with a local anesthetic (lidocaine), making a small (approximately the size of the dotted line ----- ; 1 cm) incision and removing a small (approximately 1/15th of an ounce) piece of muscle tissue. Each incision will be closed with a piece of sterile tape or a stitch, if necessary.

Sample Size Estimates and Statistical Analyses

There are no published data to guide estimates; to our knowledge, this type of study has never been done. If SERCA activity is 25% less in the metabolic syndrome, based on a standard deviation of 0.445 (Fig 14), 17 subjects per group are required (80% power, $\alpha=0.05$). We will enroll 25 for each group to account for assay problems and to increase power. For the mouse and cell culture studies, primary endpoints are clearly defined. Differences and variances from the first experiments will be used to estimate sample size (80% power, $\alpha=0.05$). All comparisons will use appropriate tests for parametric and nonparametric data. Suitable posttests will be used for multiple groups.

Anticipated Results, Alternative Approaches, Potential Problems and Benefits

Anticipated results of the study are lower SERCA activity and higher SR PC/PE ratio in people with metabolic syndrome compared to lean controls. We expect to find higher FAS and CEPT1 in metabolic syndrome skeletal muscle, reflecting activation of a phospholipid synthetic pathway attempting to replenish SR membrane composition disrupted by the obesity/high fat state.

Predicting relationships between insulin sensitivity and SERCA activity is difficult based on our mechanistic studies. The most insulin resistant could have the highest levels of FAS and CEPT1 despite lower SERCA activity in the setting of a higher PC/PE ratio. This would reflect the inability to synthesize key PE molecules due to the stress of lipid overload despite induction of the FAS-CEPT1 pathway.

An alternative approach could include euglycemic insulin clamps, but the Matsuda index is highly correlated with glucose disposal and much less invasive than a clamp.

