Study source documents will contain subject name, date of birth and other identifying information. Study data collection documents may contain subject identifier (initials and/or assigned #). Subject identifiers will be collected and maintained for internal (WU) use only. Confidential binders and study files with the subject info will be kept in a restricted access area in a locked office and a locked cabinet when not in the possession of study staff.

Withdrawal of research subjects from the protocol may occur. Research subjects will be withdrawn if any of the following occurs:

- The patient withdraws consent for any reason
- An adverse event occurs related to study procedures (i.e. severe infection from muscle biopsy)
- An adverse event that would impact any of the study results occurs. An example would be a patient who develops poison ivy during the study and requires oral steroids for control of the rash. This would disrupt their weight steady state as steroids are known to cause weight gain. Efforts will be made to adjust the study schedule to permit recovery, but if that is not possible or likely, the patient will be withdrawn.

The PI and/or sub-I will monitor each subject's lab results and visit data at each study visit.

Possible benefits to study patients would be satisfaction of altruistic values alone.

Adverse Event

An Adverse Event (AE) is any untoward medical occurrence in a study participant regardless of its relationship to study treatment.

A Serious Adverse Event (SAE) is any untoward medical occurrence that results in death, is life-threatening, requires hospitalization or prolongation of an existing hospitalization, results in persistent or significant disability, or is a congenital anomaly/birth defect. Important medical events that do not fall into the above categories may also be considered an SAE when, based on medical judgment, such events may jeopardize the patient's safety and require medical/surgical intervention to prevent one of the outcomes listed in the SAE definition. The term SAE is not intended as a measure of severity or intensity.

Adverse Events Reporting

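### Neither eligibility list addresses prior bariatric surgery or recent weight change, although the plan reports that surgical weight loss lowers FAS and CEPT1, two proteins it will compare

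*Combined protocol and SAP*

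**What the plan says.** **Effect of weight loss.** The Introduction, Background and Significance section states: "we have found that surgically induced weight loss decreases both FAS and CEPT1". The Fig 2 legend gives the source: "skeletal muscle biopsies from 16 obese human subjects before and after 20% weight loss induced by gastric bypass".

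**Role of these proteins in the study.** Under Anticipated Results, the plan says: "We expect to find higher FAS and CEPT1 in metabolic syndrome skeletal muscle".

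**Body weight as a condition for valid results.** The withdrawal list gives, as an example of an event that would affect the results, a subject who needs oral steroids for a rash: "This would disrupt their weight steady state as steroids are known to cause weight gain". The schedule may be adjusted to allow recovery; otherwise the subject is withdrawn.

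**Eligibility Criteria.** Controls are judged on sedentary status, age, BMI ("Body Mass Index (BMI) <32"), general health, screening laboratory results, medication, pregnancy and tobacco. Syndrome subjects are judged on sedentary status, age, BMI above 30, at least three ATP III items, named diseases or other major illness, medication, pregnancy and tobacco. Neither list has an item on weight history or weight-loss surgery.

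**Checks after entry.** At the two phone visits "study staff will be verifying no change in eating or exercising habits", together with medications and health status, and this is repeated at the final visit. The Schedule of Events places weight at Screening and at the final visit (Week 4). A complete history and physical examination is done at screening.

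**The concern.** The investigators' own data identify weight loss as something that changes two of the proteins they will compare, and the withdrawal example shows that they regard disturbed weight as a threat to the results. The entry criteria do not carry that through. A subject whose weight is disturbed after entry may be withdrawn, while one who was already losing weight at screening may enter.

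Three kinds of subject pass the criteria as written:

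- a formerly obese person with a past gastric bypass, now at BMI 29 and on no medication, as a control;
- a post-bypass person still above BMI 30 with three ATP III items, as a syndrome subject;
- a person who began a restrictive diet before screening, in either group, who can truthfully report no change in habits while still losing weight.

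At stake is the reading of the FAS and CEPT1 comparison. If such subjects are unevenly spread between the groups, part of an observed difference, or of its absence, would reflect weight history and not the metabolic syndrome.

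**Working it through.** **1. Is there a figure in the plan to reproduce?** Not on this point. The only sample-size figure, 17 per group, concerns SERCA activity. It cannot be reproduced because the control mean behind the 25% difference is not given. FAS and CEPT1 have no power calculation, and Fig 2 is not shown, so the size of the fall after bypass is unknown.

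**2. Do the existing checks close the gap?**

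| Safeguard | Looks back before screening? | Names surgery or weight change? | Has a limit? |
|---|---|---|---|
| Screening history and physical | Yes | No | No |
| Major-illness and health wording | In part | No | No |
| No change in habits, medication, health | No | No | No |
| Weight at Screening and Week 4 | No | Measures it | No rule uses it |

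The information is largely within reach, but nothing tells staff to act on it.

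**3. Direction of any bias in FAS and CEPT1, taken against the direction that the plan anticipates.**

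- Syndrome group: the plan expects higher levels here. Subjects whose levels have been lowered by weight loss pull the mean down, so the difference shrinks.
- Control group: the difference grows only if weight-reduced controls sit below never-obese people. The Introduction describes the pathway as one induced by obesity or a high-fat diet. Weight loss might therefore only return levels to the lean range, and then there is little or no bias.

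**4. Illustration of size.** All inputs except 25 per group are assumptions: no true group difference, normal data with SD 1, k of 25 subjects in one group lowered by s SD, and a two-sided unpaired t-test at 0.05. The group mean moves by (k/25) × s. The rejection rates come from simulation (400,000 runs per cell).

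| k of 25 | s | Mean shift | Chance of p<0.05 |
|---|---|---|---|
| 1 | 1 | 0.04 SD | 5.0% |
| 1 | 2 | 0.08 SD | 5.0% |
| 3 | 1 | 0.12 SD | 6.3% |
| 3 | 2 | 0.24 SD | 9.4% |
| 4 | 1 | 0.16 SD | 7.5% |
| 4 | 2 | 0.32 SD | 13.5% |

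The same column of mean shifts, 0.12 to 0.32 SD for 3 to 4 subjects, is the amount by which a true difference would be diluted if the affected subjects were in the syndrome group. If both groups held the same proportion of affected subjects with the same shift, there would be no expected shift between them.

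**5. Why the shift must not be treated as uniform.** Moving all 25 subjects by 0.3 SD gives an 18.0% rejection rate. But when only a fraction f is shifted, the variance of that group also rises, to 1 + f(1 − f)s². For 4 of 25 shifted by 2 SD this is 1 + 0.16 × 0.84 × 4 = 1.54, an SD of about 1.24. The wider spread offsets part of the mean shift, which is why the simulated figure is 13.5% even at a mean shift of 0.32 SD.

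**The case against.** The strongest case against is that the exposure is hypothetical and touches only secondary mechanistic measures in a study that describes itself as a pilot. Several parts of it stand.

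- A reader might infer that the whole design depends on stable weight. It does not say so: the idea appears once, in a withdrawal example, and no section makes it a design assumption.
- A reader might infer that the main comparison is biased. The sample size rests on SERCA activity, and the documents report no effect of weight loss on SERCA or PC/PE.
- A reader might infer that any weight-reduced subject has lowered FAS and CEPT1. The evidence is one before-and-after comparison in 16 people who lost 20% by gastric bypass. It does not cover dietary loss, small loss or weight that has long been stable after surgery.
- A reader might infer that post-surgical controls would manufacture the predicted result. That needs levels below those of never-obese people, which is not shown.
- The plan does more than ask about diet and exercise. It also checks medications and health status, takes a full history, has investigators review visit data and lets them remove subjects at their discretion.

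What does not stand is the suggestion that these safeguards suffice. None sets a limit on weight change or names surgery, so any exclusion on these grounds would depend on individual judgement and could differ between subjects and groups.

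**Conclusion.** The omission is real and follows from the text alone: applied exactly, the criteria admit people with the same exposure that the plan's own data link to lower FAS and CEPT1. The consequence is limited to those two measures. Dilution through the syndrome group is the more plausible direction; enlargement through the control group is possible but unsettled.

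The size cannot be derived from the documents. The range of roughly 6% to just over 13% rests on assumed numbers of affected subjects, an assumed shift of 1 to 2 SD, and all of them being in one group. With a single affected subject the error rate stays near 5%. Confidence is moderate. This is a cheap improvement worth making, not a flaw that undermines the powered comparison.

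**What to change.** For both groups:

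1. Add prior bariatric surgery to the exclusions.
2. Add a criterion of stable weight before screening, with a limit and a look-back window chosen by the sponsor, and ask about it in the screening history.
3. Compare the Screening and Week 4 weights before the biopsy against a limit set by the sponsor, and state what happens if it is exceeded.

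For subjects already enrolled, do not exclude anyone after the fact. Specify, before and blind to the assay results, a sensitivity analysis that omits those with prior bariatric surgery or with weight change beyond the limit, using the recorded history and weights.

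The cost is some eligibility wording, a few history questions and use of two weights that are already scheduled. The downside is a few more screen failures or rescheduled final visits. One limit remains: a person who lost much weight by diet well before the look-back window and is now stable would still qualify. Recording weight history would at least make such subjects visible.

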Informed consent	X					
H&P	X					
Vital signs (BP, HR, Temp)	X	X			X	
Weight	X	X			X	
Waist circumference and Height	X					
Urine Pregnancy test in women of childbearing potential	X	X			X	
Verify no change in exercise		X	X	X	X	
Verify no change in eating habits		X	X	X	X	
Verify no change in medications or health status		X	X	X	X	
CBC, CMP, HbA1c, Lipid panel	X	X				
HbA1c, Lipid panel, fasting glucose and insulin levels, as well as 3 vials of blood for future use (All drawn 5 min prior to OGTT)					X	
OGTT: 0, 30, 60, 90, 120 minutes with insulin levels also drawn at each time marker					X	
DEXA scan					X	
Leg Muscle biopsy					X	

*Subject will only have the failed test repeated.

Blood tests. Most determinations will be performed by the Washington University Core Lab for Clinical Studies, a CLIA-certified facility that has served as the reference lab for landmark clinical trials including the Coronary Primary Prevention Trial and the CARE trial. The lab will measure CBC, CMP, HbA1c, and Lipid panel at first visit and HbA1c, Lipid panel, and glucose and insulin levels, as well as 3 more vials of blood for future research at the final visit.

Oral Glucose Tolerance Test (OGTT). This test will be performed on the final visit. Study patients will be asked to arrive fasting for 10-12 hours ahead of time. An intravenous catheter will be placed, labs including Hemoglobin A1C, lipid panel, and blood glucose and insulin levels will be obtained 5 minutes prior to the start of the OGTT. Blood will be drawn for blood glucose and insulin levels at the start of the OGTT. The patient will then be asked to consume 75 grams of glucose. Blood will be drawn again for blood glucose and insulin levels at 30, 60, 90 and 120 minutes after consuming the glucose. This visit will take approximately 4-6 hours.

DEXA scan. This test will be performed on the final visit. We will ask the patient to lie on a table while they are scanned by a special machine. The DEXA scan takes about 30 minutes. DEXA images taken during the study are for specific research purposes and are not being used to

evaluate the patient's health or find medical abnormalities. These images will not be reviewed by a radiology physician to diagnose existing abnormalities.

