All AEs will be reported on the Adverse Events form that will be completed by the study staff at each regular follow-up visits. Forms will include standardized questions relating to specific events of import in patients as well as any significantly abnormal physical finding identified on examination and any significantly abnormal laboratory results obtained on the patient between visits or at the time of the visit. AEs reported or ascertained between clinic visits will be captured and reported at the time of the next scheduled visit. Pre-existing conditions (that is, conditions present prior to randomization) will not be considered or recorded as AEs unless the

condition worsens in intensity or frequency after randomization. Likewise, continuing AEs will not be reported as AEs at subsequent visits unless they increase in severity or frequency between visits, they results in criteria for a SAEs, and/or they resolve between visits. The study staff will report all AE's to HRPO according to its AE reporting policy and procedures.

Assessment of Causality and Severity

The seriousness of adverse events will be ascertained by investigator and the need for further evaluation, follow-up, or referral. The relationship between study participation and AEs will be determined according to the following criteria:

Not related – temporal relationship of the onset of the event, relative to study participation, is not reasonable or another cause can by itself explain the occurrence of the event.

Possibly related – temporal relationship of the onset of the event, relative to study participation, is reasonable but the event could have been due to another, equally likely cause.

Probably related – temporal relationship of the onset of the event, relative to study participation, is reasonable and the event is more likely explained by the study treatment than by another cause.

Definitely related – temporal relationship of the onset of the event, relative to study participation, is reasonable and there is no other cause to explain the event.

Study Data Monitoring and Safety

The study will be reviewed for safety, privacy and data integrity by the investigator(s) at regular intervals during the course of the study and at least annually by a designated Safety Officer

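### Adverse event capture depends on a next visit, but no contact follows the final visit, where the catheter and muscle biopsy are done

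*Combined protocol and SAP*

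**What the plan says.** Under Adverse Events Reporting, the recording of AEs is attached to visits. "All AEs will be reported on the Adverse Events form that will be completed by the study staff at each regular follow-up visits". For anything that happens in between, "AEs reported or ascertained between clinic visits will be captured and reported at the time of the next scheduled visit". The same section adds a duty with no visit window: "The study staff will report all AE's to HRPO according to its AE reporting policy and procedures".

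The visit plan is under Study procedures and in the Schedule of Events. After screening in Week 1, eligible subjects "will receive 2 phone calls (Visits 2 and Visit 3) approximately 1 week apart", in Weeks 2 and 3, and then "will return to the study site for a final subsequent visit" in Week 4. The Week 4 column is the last one.

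Both invasive procedures of interest belong to that last visit. For the OGTT, which is scheduled there, "An intravenous catheter will be placed". Of the muscle biopsy the protocol says: "This procedure will be performed on the final visit".

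The protocol foresees complications. The section on potential problems lists infection or injury from the biopsy and likens catheter risk to that of blood drawing, for which it names infection and clotting. The withdrawal criteria give severe biopsy infection as an example of a procedure-related event. Under Data Collection and Quality Assurances, subjects are asked to contact staff about events arising between clinic visits.

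**The concern.** A rule that records events at the next visit works only while a next visit exists. Here the most invasive procedure is placed at the last contact, so the rule has nothing to attach to in the period when a wound or catheter-site infection could appear after the subject has gone home. The screening blood draw, a lesser procedure, is followed by two calls that check for a change in health status; the biopsy is followed by none.

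What is at stake is the safety record, not the scientific comparison. PI review, reports to HRPO and the Safety Officer's annual decision on continuing or stopping all work from events that have reached the study staff. If nobody asks after the biopsy, a listing without delayed infections cannot separate subjects who had none from subjects who did not report one.

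**Working it through.** The plan gives no figure on this point to reproduce. The check lays the schedule against the timing of the procedures and against each AE provision.

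**Scheduled contacts per subject (Schedule of Events, optional rescreen excluded)**

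| Week | Contact | Type | Catheter and biopsy |
|---|---|---|---|
| 1 | Screening | Clinic | No |
| 2 | Visit 2 | Phone | No |
| 3 | Visit 3 | Phone | No |
| 4 | Final visit | Clinic | Yes, both |

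- Contacts in total: 2 clinic + 2 phone = 4.
- Contacts after Week 4: 0 of 4. The optional rescreen also precedes the final visit, so it does not change this.
- Interval between the two clinic visits: Week 4 − Week 1 = about 3 weeks, all of it before the biopsy.

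**Subjects concerned.** The sample size section says: "We will enroll 25 for each group to account for assay problems and to increase power". So 2 × 25 = 50 biopsied subjects at most.

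**AE provisions, applied to an event that appears some days after Week 4**

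1. *AE form at follow-up visits:* no follow-up visit remains.
2. *Capture at the next scheduled visit:* none exists, whether or not phone calls count as visits.
3. *Self-report request (Data Collection and Quality Assurances):* worded for the time between clinic visits. Apart from a rescreen, the only such interval ends at the biopsy visit, so read literally the request does not reach the time after it.
4. *PI review and reports to HRPO:* these apply to events that become known. One PI-review sentence names only events at or between study visits; others have no window. None contacts a subject.
5. *Safety Officer (annual and ad hoc) and continuous review:* these act on accumulated data. None contacts a subject.
6. *Stated collection period:* no end is given. The only time anchor in the section is randomization, used to define pre-existing conditions, and this cross-sectional study does not randomize.

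**What follow-up would allow.** If all 50 subjects were followed and none had a delayed event, the exact one-sided 95% upper bound on the risk would be 1 − 0.05^(1/50) = 0.058, or 5.8%. Without ascertainment after the biopsy, that statement could not be made from an empty listing. This is context only and is not an estimate of missed events.

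**The case against.** The best case for the plan is that its AE system still works after Week 4, but passively. Staff must send all AEs to HRPO and the PI reviews all reported AEs, neither limited to a visit window; the Safety Officer can review ad hoc. Subjects are asked to call, and it is a strict reading to hold that a text loose enough to mention randomization in an observational study meant to exclude calls after the biopsy. The consent pages and the HRPO policy are not in the copy reviewed and may carry instructions on wound problems. No event rate is given, the incision is about 1 cm, the study gives no treatment, and the protocol never promises active follow-up after the biopsy, so an added call repairs no broken commitment. On this view the point is a minor clarification.

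Much of this stands. Late events can be reported and, once known, would be handled. What the consent form says is unknown, and no harm can be put into numbers. But none of these provisions contacts a subject after the biopsy. An instruction in the consent form would still leave capture to the subject's initiative; it would neither create a scheduled contact nor give the visit-based rule a visit to use. The loose wording explains how the gap may have arisen but does not close it.

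**Conclusion.** The concern holds. Followed as written, the protocol has no scheduled contact and no stated AE collection period after the visit at which the catheter and biopsy are done: 0 of 4 contacts, for up to 50 subjects. Its capture rule for between-visit events cannot operate for delayed events from its most invasive procedure.

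The finding is limited to active ascertainment. Events on the day can be recorded at the final visit, and later events that reach staff are covered. No under-count is estimated, because the documents give no complication rate. The SERCA and PC/PE comparisons are not affected. The conclusion rests on the protocol text and its Schedule of Events as supplied; consent-form or HRPO instructions could strengthen self-report but were not available. The change should be made, since it is cheap and the protocol itself foresees these complications.

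**What to change.** 1. In Adverse Events Reporting, state an AE collection period that extends past the final visit, and reword the capture sentence so that it covers events after the last visit. The period also needs a starting point that this study has, in place of randomization.
2. Add one AE-ascertainment phone contact after the final visit to the Schedule of Events, using the phone process already in place for Visits 2 and 3. The investigator should set the timing.
3. In Data Collection and Quality Assurances, extend the self-report request to events after the final visit.

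Items 1 and 3 close the gap in the text; item 2 supplies the active ascertainment that wording alone cannot.

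The cost is at most 2 × 25 = 50 short calls, one added column in the Schedule of Events and edits to two sections, with no new procedure or staff. Subjects who cannot be reached by phone would still depend on self-report.
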